3.2. Discussion and Rationale for Study Design

The prognosis for patients with advanced BTC is very poor, with an estimated 5-year survival rate of approximately 5 to 15% for all patients (Valle 2017). Gemcitabine combined with a platinum agent has become the recognized standard regimen for first-line treatment of patients with advanced BTC (Okusaka 2010, Valle 2010). In the second-line setting, results of a recent Phase 3 trial (the ABC-06 Study) showed a median OS benefit of 0.9 months for subjects treated with mFOLFOX plus ASC compared with those who received ASC alone (HR 0.69, 95% CI: 0.50, 0.97, $p = 0.031$). However, mFOLFOX treatment was associated with a higher rate of Grade 3/4 AEs (59% vs. 39%) and 3 of 81 treated subjects died from chemotherapy-related toxicities (Lamarca 2019). Other than the ABC-06 trial, there are no other published randomized data in the second-line and later BTC setting. Pemigatinib was granted approval for the treatment of patients with previously treated, unresectable locally advanced or metastatic cholangiocarcinoma based on ORR and DOR. In the FIGHT-202 trial, 107 subjects were treated in the open-label, single-arm study. The ORR was 36% (95% confidence interval [CI]: 27, 45), with a median DOR of 9.1 months (95% CI: 6.0, 14.5) (PEMAZYRE™).

Studies have shown that HER2 is over-expressed in BTC, and HER2-targeted agents demonstrate clinical activity in tumors that harbor HER2 over-expression or amplification (Kiguchi 2001, Nakazawa 2005, Treekitkarmmongkol 2010, Galdy 2017) and (Nam 2016). However, no HER2-targeted agents are approved for treatment of patients with BTC. Given the high unmet medical need for this patient population and the promising anti-tumor activity and tolerability of zanidatamab monotherapy in BTC, a single-arm study design is considered appropriate.

Data from studies in other pathologies indicate that antibody targeting of HER2 is most effective in disease that is HER2 amplified and shows intermediate-to-high levels of protein expression by IHC. In the ToGA study 22.4% of enrolled subjects had FISH positive/IHC 0 or FISH positive/IHC 1+ disease (Bang 2010). A post-hoc exploratory survival analysis failed to show a trend for benefit from the addition of trastuzumab to frontline chemotherapy (Bang 2010). The recently reported results of the colorectal cohort of the MyPathway study that treated 57 subjects with HER2 amplified disease demonstrated an overall ORR of 32% (18/57 subjects). However, no objective responses were observed in the 8 subjects who did not have high levels of protein expression by IHC (Meric-Bernstam 2019). The primary efficacy population for the current study will therefore comprise subjects with disease that is HER2 amplified by ISH and IHC 2+ or 3+ (Cohort 1, N = 75; see Section 3.1). To evaluate the activity of zanidatamab in subjects with lower levels of HER2 expression, subjects with disease that is HER2 amplified by ISH and IHC 0 or 1+ will also be enrolled (Cohort 2, N = 25; see Section 3.1).

The primary endpoint of this study, confirmed ORR, is a direct measure of antitumor activity and is an acceptable endpoint that may be evaluated in a single-arm study according to the FDA Guidance for Industry “Clinical Trial Endpoints for the Approval of Cancer Drugs and Biologics” (December 2018).

Standardized RECIST 1.1 criteria (Eisenhauer 2009) will be employed to evaluate disease responses during the study, and all imaging assessments will be submitted to an independent third-party imaging core laboratory to ensure consistent unbiased application of the RECIST 1.1 criteria. Investigator-determined responses will be confirmed by repeat scans performed 4 weeks after initial documentation of response. Every effort should be made to confirm disease progression radiographically whenever possible. Only in instances where subjects appear to have unequivocal clinical progression and it is not possible or feasible for the subject to undergo radiologic assessment should investigators remove the subject from study treatment. Local assessment of disease response will be used for subject management and treatment decisions. To further assess the clinical significance of ORR in this study, DOR will be evaluated as a secondary endpoint.

3.2.1. Method of Assigning Subjects to Treatment Groups

This is a single-arm study that will enroll subjects into 2 separate cohorts.

3.2.2. Rationale for Selection of Doses

All subjects in the study will receive 20 mg/kg zanidatamab given IV Q2W. This dose was a recommended dose from the monotherapy part of the Phase 1, dose-escalation study of zanidatamab (ZWI-ZW25-101).

3.2.3. Blinding

This is an open-label study.

4. STUDY POPULATION

Subjects must meet all of the enrollment criteria to be eligible for this study. Eligibility criteria may not be waived by the investigator and are subject to review in the event of a Good Clinical Practice (GCP) audit and/or health regulatory authority inspection.

4.1. Inclusion Criteria

1. Histologically- or cytologically-confirmed BTC, including ICC, ECC, or GBC.
2. Locally advanced or metastatic BTC and not eligible for curative resection, transplantation, or ablative therapies.
3. Received at least 1 prior gemcitabine-containing systemic chemotherapy regimen for advanced disease, and experienced disease progression after or developed intolerance to the most recent prior therapy. For subjects who received gemcitabine in prior adjuvant or neoadjuvant treatment, if progression occurred < 6 months from the latter of primary surgical resection or completion of gemcitabine-containing adjuvant therapy, they will be considered as having received 1 prior line of therapy for advanced disease.
4. Subjects must have at least 1 measurable target lesion by RECIST 1.1. Subjects who have received prior local therapy (embolization, chemoembolization, radiofrequency ablation, or radiation therapy) are eligible provided measurable disease falls outside of the treatment field or is within the treatment field and has shown $\geq 20\%$ growth in size since post-treatment assessments.
5. Subjects must test positive for HER2 amplification by in situ hybridization (ISH) assay at a central laboratory on a new biopsy or archival tissue. Note that fine needle aspirates (FNAs; cytology samples) and biopsies from sites of bone metastases are not acceptable. Testing may occur at any time after diagnosis of advanced or metastatic disease and before study enrollment.
6. Male or female, ≥ 18 years of age (or the legal age of adulthood per country-specific regulations).
7. ECOG PS ≤ 1 .
8. Adequate hematologic function, defined as absolute neutrophil count (ANC) $\geq 1.5 \times 10^9/L$, platelet count $\geq 75 \times 10^9/L$ (not requiring transfusion support), and hemoglobin (Hgb) ≥ 9 g/dL (subjects with chronic anemia that is supported by intermittent red blood cell [RBC] transfusions are eligible).
9. Liver function: serum bilirubin ≤ 1.5 x the upper limit of normal (ULN) or ≤ 3 x ULN for subjects with Gilbert's disease, aspartate aminotransferase (AST) ≤ 3 x ULN, and alanine aminotransferase (ALT) ≤ 3 x ULN. For subjects with liver involvement, AST, and ALT ≤ 5.0 x ULN is acceptable.
10. Adequate cardiac function, as defined by LVEF $\geq 50\%$.

11. Kidney function: glomerular filtration rate (GFR) \geq 30 mL/min as estimated by the Modification of Diet in Renal Disease (MDRD) equation (see [Section 7.8.3](#)).
12. Females of childbearing potential must have a negative serum or urine beta human chorionic gonadotropin (β -hCG) pregnancy test result within 3 days prior to the first dose of zanidatamab. Females with false positive urine test results can be enrolled if subsequent serum testing is negative (see [Section 4.3](#)).
13. For female subjects of childbearing potential and for male subjects with a partner of child-bearing potential, willingness for the couple to use 2 methods of birth control with a failure rate of less than 1% per year during the study and for 12 months after the last dose of zanidatamab (see [Section 4.3](#)).
14. Male subjects must agree to not donate sperm and female subjects must agree to not donate oocytes starting at screening and throughout the study period, and for at least 12 months after the last dose of zanidatamab (see [Section 4.3](#)).
15. The subject or subject's legally acceptable representative must provide written informed consent. Subjects who elect to be pre-screened for HER2 status must sign a separate written informed consent for collection, storage, and analysis of the tumor tissue.

4.2. Exclusion Criteria

Subjects will be excluded from the study if 1 or more of the following criteria are applicable:

1. Received systemic anti-cancer therapy within 3 weeks of the first dose of zanidatamab. Received radiotherapy within 2 weeks of the first dose of zanidatamab.
2. Had major surgery within 4 weeks of the first dose of zanidatamab.
3. Prior treatment with HER2-targeted agents.
4. Untreated central nervous system (CNS) metastases, symptomatic CNS metastases, or radiation treatment for CNS metastases within 4 weeks of start of study treatment. Stable, treated brain metastases are allowed (defined as subjects who are off steroids and anticonvulsants and are neurologically stable with no evidence of radiographic progression for at least 4 weeks at the time of screening).
5. Known leptomeningeal disease (LMD). If LMD has been reported radiographically on baseline MRI, but is not suspected clinically by the investigator, the subject must be free of neurological symptoms of LMD.
6. Concurrent uncontrolled or active hepatobiliary disorders or untreated or ongoing complications after laparoscopic procedures or stent placement, including but not limited to active cholangitis, unresolved biliary obstruction, infected biloma or abscess. Any complications must be resolved more than 2 weeks prior to the first dose of zanidatamab.
7. Prior or concurrent malignancy whose natural history or treatment has, in the opinion of the investigator or medical monitor, the potential to interfere with the safety or efficacy assessment of the investigational regimen.
8. Significant acute infection or chronic infections that have not stabilized with treatment.
9. Active hepatitis, including the following criteria:

- a Acute or chronic hepatitis B (Exception: subjects who are hepatitis B surface antigen positive are eligible if they have HBV DNA less than 500 IU/mL)
 - b Infection with hepatitis C (Exception [i] subjects who have no history of curative viral treatment and are documented to be viral load negative are eligible; [ii] subjects who have completed curative viral therapy \geq 12 weeks prior to enrollment, and viral load is negative are eligible)
10. Infection with human immunodeficiency virus (HIV)-1 or HIV-2 (Exception: subjects with well-controlled HIV [e.g., CD4 $>$ 350/mm³ and undetectable viral load] are eligible).
 11. Females who are breastfeeding or pregnant, and females and males planning a pregnancy.
 12. History of life-threatening hypersensitivity to monoclonal antibodies or to recombinant proteins or excipients in the drug formulation of zanidatamab.
 13. Treatment with anthracyclines within 90 days before first dose of zanidatamab and/or total lifetime load exceeding 360 mg/m² Adriamycin[®] or equivalent.
 14. Use of corticosteroids administered at doses equivalent to $>$ 15 mg per day of prednisone within 2 weeks of first zanidatamab dosing unless otherwise approved by the medical monitor. Topical, ocular, intra-articular, intranasal, and/or inhalational corticosteroids are permitted.
 15. Ongoing, clinically significant toxicity (Grade 2 or higher) associated with prior cancer therapies, with the following exceptions:
 - a Alopecia
 - b Congestive heart failure (CHF), which must have been \leq Grade 1 at the time of occurrence and which must have completely resolved
 - c Grade 2 peripheral sensory neuropathy
 16. QTc Fridericia (QTcF) $>$ 470 ms.
 17. History of myocardial infarction or unstable angina within 6 months prior to enrollment, troponin levels consistent with myocardial infarction, or clinically significant cardiac disease, such as ventricular arrhythmia requiring therapy, uncontrolled hypertension, or any history of symptomatic CHF.
 18. Acute or chronic uncontrolled pancreatitis or Child-Pugh Class C liver disease.
 19. Any other medical, social, or psychosocial factors that, in the opinion of the investigator, could impact safety or compliance with study procedures.

4.3. Childbearing Potential and Contraception

4.3.1. Definitions

A person of childbearing potential is anyone born female who has experienced menarche and who has not undergone surgical sterilization (e.g., hysterectomy, bilateral salpingectomy, bilateral oophorectomy) or has not completed menopause. Menopause is defined clinically as no menses for 12 months without an alternative medical cause. A high follicle stimulating hormone

(FSH) level in the postmenopausal range may be used to confirm a post-menopausal state in women not using hormonal contraception or hormonal replacement therapy. However, in the absence of 12 months of amenorrhea, a single FSH measurement is insufficient.

A man is considered fertile after puberty unless permanently sterile by bilateral orchidectomy.

According to the inclusion and exclusion criteria, pregnant or breastfeeding subjects cannot be included in the study, and adequate contraceptive measures should be taken to prevent female subjects of childbearing potential or female partners of male subjects (either of whom are of childbearing potential) from getting pregnant from the time of signing informed consent, during study participation and for at least 12 months after the last dose of study drug (see [Section 4.3.2](#)). Subjects will be instructed that known or suspected pregnancy occurring during this same period of time should be reported to the investigator, regardless of when the pregnancy was confirmed. If a female subject is pregnant, the investigator will immediately discontinue the subject from the study. Upon discontinuation, only those procedures that would not expose the subject to undue risk will be performed.

In the event that a female subject or female partner of a male subject is found to be pregnant after inclusion in the study, the pregnancy will be followed to term with subject/partner consent, and the status of the mother and child will be reported to the sponsor after delivery.

Details of the pregnancy will be recorded on the withdrawal page of the case report form (CRF), and a Pregnancy Report Form will be completed.

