Subjects may continue on treatment with zanidatamab until investigator-determined radiographic disease progression per RECIST 1.1, unequivocal clinical progression, unacceptable toxicity, consent withdrawal, physician decision, pregnancy, start of a subsequent anticancer therapy, or study termination by the sponsor. Unequivocal clinical progression is defined as worsening or re-emergence of pre-existing symptoms relating to underlying cancers (e.g., increase in disease-related pain), or emergence of new symptoms that cannot be attributed to study drug toxicities or alternative causes. A marked deterioration in ECOG performance status may also indicate unequivocal clinical progression. Every effort should be made to confirm disease progression radiographically. Only in instances where subjects appear to have unequivocal clinical progression and it is not possible or feasible for the subject to undergo radiologic assessment should investigators remove the subject from study treatment. Subjects who discontinue treatment with zanidatamab for any reason should enter the 30-day safety follow-up period, and will continue with efficacy follow-up (if treatment discontinuation was due to reasons other than progressive disease or start of subsequent anticancer therapy) as well as survival follow-up.

Efficacy Assessments

CT and/or MRI scans will be performed at baseline and Q8W during treatment (timed from Cycle 1 Day 1) and will continue after treatment discontinuation every 8 weeks until disease progression or start of subsequent anticancer therapy. Disease response will be assessed according to RECIST 1.1 by ICR (primary endpoint) and investigator (secondary endpoint); responses are to be confirmed 4 weeks following initial documentation of objective response by the investigator.

Pharmacokinetic and Immunogenicity Assessments

Blood samples will be collected at protocol-specified timepoints for evaluation of serum concentrations (PK) of zanidatamab and for evaluation of ADA (immunogenicity).

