Enrolled subjects will receive zanidatamab, 20 mg/kg given intravenously (IV) Q2W until 1 of the treatment discontinuation criteria is met (see [Section 4.4.1](#)). Unequivocal clinical progression is defined as worsening or re-emergence of pre-existing symptoms relating to underlying cancers (e.g., increase in disease-related pain), or emergence of new symptoms that cannot be attributed to study drug toxicities or alternative causes. A marked deterioration in ECOG PS may also indicate unequivocal clinical progression. Subjects who discontinue treatment with zanidatamab for reasons other than progressive disease or start of subsequent anticancer therapy will continue in follow-up with disease assessments approximately every 8 weeks after the previous scan until disease progression or start of subsequent anticancer therapy. Responses that are initially observed during this follow-up period should be confirmed with disease assessment 4 weeks later. Following progression or start of subsequent anticancer therapy, disease assessments will be discontinued, and subjects will enter long-term follow-up for survival status. Data on survival will be collected via clinic visits (if feasible) or via telephone calls every 3 months after the last follow-up visit. Subjects may be discontinued from the study due to death, lost to follow-up, consent withdrawal, or study termination by sponsor.

Computed tomography (CT) and/or magnetic resonance imaging (MRI) scans will be performed at baseline and every 8 weeks (Q8W) during treatment timed from Cycle 1 Day 1 and will continue after treatment discontinuation every 8 weeks until disease progression or start of subsequent anticancer therapy. Disease response will be assessed according to RECIST 1.1 by ICR (primary endpoint) and investigator (secondary endpoint); responses are to be confirmed 4 weeks following initial documentation of objective response by the investigator.

[figure not shown]

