4.4.1. Treatment Discontinuation

Study treatment may be discontinued for any of the following reasons:

- AE
- Death

- Lost to follow-up
- Withdrawal by subject
- Physician decision (non-AE, non-progressive disease [PD])
- Pregnancy
- PD (either radiographic or unequivocal clinical progression; see [Section 7.2](#))
- Study termination by sponsor
- Other, non-AE

If a subject has not received zanidatamab for more than 4 weeks due to an AE, the investigator should contact the medical monitor to discuss whether the subject should continue to receive study treatment.

If a subject starts subsequent non-study anti-cancer therapy, study treatment must be discontinued before the start of the new therapy.

At a minimum, all efforts should be made for subjects to complete the End of Treatment (EOT) visit ([Section 6.4](#)) and the safety follow-up visit ([Section 6.5](#)).

Subjects who discontinue treatment with zanidatamab for reasons other than progressive disease or start of subsequent anticancer therapy will continue in follow-up with disease assessments approximately every 8 weeks after the previous scan until disease progression or start of subsequent anticancer therapy. Following progression or start of subsequent anticancer therapy, disease assessments will be discontinued, and subjects will enter long-term follow-up for survival status.

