4.4.2. Subject Withdrawal from Study

Subjects may be discontinued from the study for any of the following reasons:

- Lost to follow-up
- Death
- Withdrawal of consent
- Study termination by sponsor

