5.3. Duration of Study Treatment

Subjects may continue on study treatment until investigator-determined radiographic disease progression per RECIST 1.1, unequivocal clinical progression, unacceptable toxicity, consent withdrawal, physician decision, pregnancy, start of a subsequent anticancer therapy, or study termination by the sponsor. Every effort should be made to confirm disease progression radiographically. Only in instances where subjects appear to have unequivocal clinical progression and it is not possible or feasible for the subject to undergo radiologic assessment may investigators remove the subject from study treatment.

Subjects who discontinue treatment with zanidatamab for any reason should enter the 30-day follow-up period, as well as survival follow-up.

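### Protocol 4.3.1 removes a pregnant subject from the study, while every other relevant section treats pregnancy as a reason to stop zanidatamab and continue follow-up

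*Protocol*

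**What the plan says.** Protocol 4.3.1, in the section on childbearing potential, gives a mandatory instruction: "If a female subject is pregnant, the investigator will immediately discontinue the subject from the study". The sentence after it reads: "Upon discontinuation, only those procedures that would not expose the subject to undue risk will be performed". Shortly before it, 4.3.1 sets the period for contraception and for reporting a pregnancy, which runs from consent, "during study participation and for at least 12 months after the last dose of study drug". The section then has the pregnancy followed to term, with consent, and its details recorded on the withdrawal page of the case report form.

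Other sections treat pregnancy as a reason to stop the drug. The list of events that end treatment, in both the synopsis (Duration of Treatment) and 5.3, includes "consent withdrawal, physician decision, pregnancy, start of a subsequent anticancer therapy, or study termination by the sponsor". Section 4.4.1 opens with "Study treatment may be discontinued for any of the following reasons" and has pregnancy among its bullets. Section 5.3 then adds: "Subjects who discontinue treatment with zanidatamab for any reason should enter the 30-day follow-up period, as well as survival follow-up".

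Leaving the study is handled separately. Section 3.1 states: "Subjects may be discontinued from the study due to death, lost to follow-up, consent withdrawal, or study termination by sponsor". Section 4.4.2 opens with "Subjects may be discontinued from the study for any of the following reasons" and lists the same four reasons.

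**The concern.** The protocol distinguishes two actions with different consequences. A subject who stops treatment stays under observation; a subject who leaves the study does not. Section 4.3.1 prescribes the second action for an event that the rest of the protocol assigns to the first.

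A site that follows 4.3.1 as written could end survival follow-up, and efficacy follow-up where imaging is safe, for a treated subject who is still willing to be followed. Pregnancy safety does not require this loss, since a telephone call or a check of records carries no risk to her. In the analysis, her overall survival could be censored early, at the date she was last known alive (SAP 8.2.7). If she had not progressed, PFS and, for a responder, duration of response would be censored at the last adequate assessment (SAP Table 6 and 8.2.6). The site would also have a reason for study exit that 4.4.2 does not provide for.

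**Working it through.** No formula applies and the plan gives no figure to reproduce. The check sets the relevant lists in the current protocol text side by side and asks whether pregnancy appears in each.

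| Protocol section | What the list governs | Entries | Pregnancy listed? |
|---|---|---|---|
| Synopsis, Duration of Treatment | end of treatment | 8 | yes |
| 5.3 | end of treatment | 8 | yes |
| 4.4.1 | end of treatment | 9 | yes |
| 3.1 | leaving the study | 4 | no |
| 4.4.2 | leaving the study | 4 | no |
| 6.6 | end of efficacy follow-up | 2 (progression, subsequent therapy) | no |
| 6.7 | end of survival follow-up | 5 (death, loss to follow-up, consent withdrawn, study completed, sponsor termination) | no |

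All three treatment lists include pregnancy. None of the four lists on study exit or end of follow-up does. Section 4.3.1 stands alone.

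**Can 4.3.1 be reconciled with the rest?** Take a subject on zanidatamab who becomes pregnant. Under 4.4.1 and 5.3 she stops the drug. Under 5.3 she then enters the 30-day period and survival follow-up. Under 6.6 she also continues disease assessments, because she stopped for neither progression nor new therapy. Under 6.7 survival contact runs until one of its five conditions is met. Under 4.3.1, read literally, she leaves the study at once. Both cannot be done.

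**A subject already off treatment.** The reporting period in 4.3.1 extends at least 12 months beyond the last dose. If the disputed sentence is applied over that period, it also reaches a subject in follow-up. She has no treatment to stop, so the only thing left to discontinue is follow-up.

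**Does the next sentence of 4.3.1 resolve it?** It restricts procedures after discontinuation to those without undue risk. That permits follow-up but does not require any.

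**Size.** The documents give no pregnancy rate. Assuming one such subject in Cohort 1, the share of the planned overall survival analysis is 1/75 = 1.3%. The primary response rate is barely touched: every treated subject stays in the Cohort 1 denominator (Protocol 9.3, Table 13), and imaging may be limited for undue risk under either wording.

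**The case against.** The strongest reply is that 4.3.1 uses the word *study* loosely for study treatment and that the operative sections are clear. The synopsis, 5.3 and 6.7 supply the duty to follow up, and 4.3.1 only limits risky procedures. The same section expects procedures after discontinuation and follows the pregnancy to term, which fits poorly with a complete exit. The reference to a withdrawal page settles nothing, because 4.4, 6.4 and Table 9 also use *withdrawn* for stopping treatment. All of this is fair, and it is probably what was intended. But it does not change what the sentence orders: the instruction is mandatory and a site is entitled to follow it.

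A second reply is that the case of a subject already off drug is remote. The last scheduled pregnancy test is at the 30-day visit, and 7.8.1.2 handles later pregnancies through a report form without mentioning study exit. That is true and makes the case less likely, but the conflict for subjects on treatment does not depend on it.

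A third reply concerns survival. SAP 8.2.7 equates the date last known alive with the date of last contact, and the mother's status is reported after delivery. Pregnancy follow-up could therefore preserve vital status until then, leaving only later survival time at risk. This reduces the possible loss, provided that she consents to pregnancy follow-up and that such contacts enter the survival data. It does not remove the loss.

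Finally, no hypothesis is tested and overall survival is a descriptive secondary endpoint, so no formal decision depends on one subject. That is correct and is reflected in the grading.

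**Conclusion.** The point holds as a minor internal inconsistency. Section 4.3.1 cannot be followed literally alongside 4.4.2, 5.3, 6.6 and 6.7, and neither redaction nor the amendment history explains the difference.

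The practical effect is small. Contraception requirements, testing on Day 1 of each cycle and the exclusion of people planning pregnancy should make the event rare, although its frequency cannot be estimated from the documents. The 1.3% figure assumes one case in a cohort of 75 and is not a forecast. Safety information is largely protected: 6.5 gives all subjects a 30-day visit, 7.8.1.3 continues follow-up of adverse events, and 4.3.1 follows the pregnancy itself. What remains exposed is survival follow-up, and efficacy follow-up where imaging is safe, for a subject who has not withdrawn consent.

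**What to change.** In 4.3.1, have the investigator discontinue a pregnant subject from study treatment instead of from the study. Add one sentence saying that 30-day safety, survival and pregnancy follow-up continue unless consent is withdrawn, and that efficacy imaging is done only as far as it poses no undue risk. A subject already off zanidatamab would then simply remain in follow-up.

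The cost is one phrase and one sentence, in the next amendment or a clarification letter to sites. No procedures are added and no analysis changes.
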